2.2. Intended use

The objective for TIES® is to provide a continent, sanitary, odourless system to be used in various patient groups investigated in previous studies:

- Patients with diseases such as ulcerative colitis, familial adenomatous polyposis coli, multiple colonic cancers or other diseases requiring elective colectomy followed by a permanent ileostomy, ileo rectal anastomosis or ileal pouch-anal anastomosis.
- Patients with a failing conventional ileostomy, continent ileostomy, ileo-rectal anastomosis or ileal pouch-anal anastomosis.

Patients with Crohn's disease will not be enrolled in the trial.

The implant or TIES® Port is used to construct a stoma by implantation in the abdominal wall, penetrating the skin, and is anchored in the dermal and subcutaneous tissues. The ileum outlet is passed through the implant. The internal mesh structure in the TIES® Port implant facilitates a biological attachment of the bowel segment to the implant. The Turnbull Adaptor is clipped on the cylinder top of the TIES® Port. It is used during the first weeks to provide optimum in-growth conditions by securing the ileum above the TIES® Port. The Stabilizer is positioned around the implant in order to secure the implant and provides support above skin level during the in-growth period.

CLINICAL INVESTIGATION PLAN

During the first weeks, patients will have to use standard stoma bags. Below is a drawing (Figure 10) of a cross section of abdominal wall displaying the TIES® Port connected to a conventional ileostomy stoma.

[figure not shown]

Figure 10 Cross-section showing the ileum connected to the TIES Port (no Lid attached).

After about four weeks the intestine has grown enough into the implant for the Turnbull Adaptor to be removed, if the Turnbull Adaptor has not already detached by itself from the stoma.

The part of the intestine protruding outside the implant has now started to wizen and, if necessary, is trimmed away by the surgeon in a simple procedure if required and the intestine will now reside permanently just at the top of the implant.

Once the implant is healed and fully integrated into the tissue, the top of the implant can be closed with a TIES® Lid. The TIES® Lid has an integrated emptying hole which can easily be opened and closed. Together with a TIES Emptying Pouch, this allows for the system to be emptied in a soil-free procedure.

Figure 11 The ileostomy is being emptied with an irrigation sleeve.

2.3. Manufacturing

The manufacturing of the Port is subcontracted by OstomyCure AS to 3DSystems, an ISO13485 approved medical device subcontractor. The TIES® Port is sterilized with steam sterilisation by autoclaving. Please refer to the Investigators Brochure for more detailed manufacturing information of all system parts.

CLINICAL INVESTIGATION PLAN

2.4. Training

The Sponsor is responsible for providing site personnel with the information and training they need to conduct the study properly. Study-specific training and education is required for all site staff with roles in this trial. The Sponsor is responsible for maintaining documentation of attendance at each of the training sessions provided.

The Sponsor personnel will provide training and technical support on the TIES® System and procedure to the Investigator and other health care personnel as needed before and during procedure and testing required by the protocol. In addition, the Sponsor personnel may perform certain activities to ensure study quality. These activities may include the following.

- Observing testing or medical procedures to provide information relevant to protocol compliance
- Reviewing collected data and study documentation for completeness and accuracy on the performance of the procedure

3. STUDY DESIGN

This is a multi-center, open study that evaluates the safety, performance and durability of the TIES® transcutaneous titanium implant to 12-months post implantation.

This study will be conducted in accordance with the Standard ISO 14155 and other legal requirements.

3.1. Rationale for the Study Design

As discussed previously, there are currently 3 different surgical approaches for patients requiring a permanent ileostomy, namely pelvic pouch, continent ileostomy and conventional ileostomy. The choice of the procedure is based on individual needs. The TIES® system offers a unique function in that the TIES® Port allows the use of a TIES® Lid to control intestinal emptying as required, as an alternative to using stoma bag to collect waste continuously from conventional ileostomy. It is also indicated as a treatment for patients with failed pelvic pouch or continent ileostomy. A single arm study is appropriate in this context.

The TIES® Port is implanted transcutaneously so that it becomes part of the stoma to a conventional ileostomy. A pre-requisite for success is to engage only surgeons who are skilled in performing ileostomy.

The study population includes patients with ulcerative colitis, familial adenomatous polyposis coli, other diseases requiring elective colectomy with a permanent ileostomy, or patients requiring a permanent ileostomy; or patients with a medical need for an alternative to an existing conventional ileostomy, continent ileostomy or pelvic pouch.

Only limited conclusions on outcomes can be drawn from the two previous studies because most enrolled subjects were converted from pelvic pouch, continent ileostomy or had complications associated with previous conventional ileostomy. It is relevant to study more patients who have not undergone previous complicated abdominal surgeries. By enrolling 200 subjects, this gives an opportunity to enrol patients undergoing ileostomy for the first time without needing conversion from pelvic pouch, continent ileostomy or pre-existing ileostomy complicated by incisional or parastomal hernia.

The objective of the study is to collect data to evaluate the safety, performance, durability of the implant and impact on quality of life in a group of subjects needing a permanent ileostomy

CLINICAL INVESTIGATION PLAN

(as described in the intended use). Acceptability of the implant to study subjects is part of performance evaluation. Because the subject will need to use a stoma bag in the initial healing phase, subject's preference for the TIES® solution for continence control versus stoma bag can be evaluated in this single-arm study.

This protocol plans for five interim data analyses. The first two interim analysis are planned after collection of 8-week results from the first 5 and of 24-week results of the first 20 subjects respectively, to review all available study data and to assess if there is a need to modify the study protocol including adjusting the collection of outcome measurements for performance assessment. The third, fourth and fifth interim analyses will be conducted when 50, 100 and 150 subjects, respectively, have completed 24 weeks follow-up in order to assess the primary and secondary 24-week safety and performance endpoints, make a preliminary assessment of the types of patient with high device acceptability, and consider whether some of the secondary study instruments (e.g. Quality of Life Questionnaires) can be dropped for the remaining patients to simplify follow-up and reduce burden on patients and clinical teams.

The final analysis will be carried out after the last subject has completed the 52-week assessment.

3.2. Participating Sites and Study Population

Up to 25 sites will be enrolling in up to 6 countries in Europe and Asia. A minimum of 200 patients will be enrolled, with a history of ulcerative colitis, familial adenomatous polyposis coli, other diseases requiring elective colectomy with a permanent ileostomy, or patients with a failing conventional or continent ileostomy or pelvic pouch. This study population is representative of the devices intended target population. These patients will be followed for 12 months after the implantation procedure. Enrolment is expected to take approximately 48 months due to Covid-19

4. STUDY OBJECTIVE AND ENDPOINTS

The primary objective is to evaluate the safety, performance and durability of the TIES® Port to 52 weeks in subjects after implantation. The secondary objective is to evaluate Quality of Life (QoL) in subjects implanted with the TIES® Port.

4.1. Performance Evaluation

Performance evaluation is based on subject's assessment of performance as recorded on the 3-day diary preceding each scheduled follow-up at 16, 24, 36 and 52 weeks after operation. Performance evaluation applies only among subjects with the TIES® Port *in situ*.

Among subjects with the TIES® Port *in situ*, performance will be assessed according to (a) the proportion of subjects who use the TIES® Lid for continence control; (b) the proportion of subjects experiencing visible leakages around the implant; and (c) subject's assessment on the ease of use of the TIES® Solution.

Primary endpoint is absence of visible leakage or fecal staining of clothing at 24 weeks after implantation of the TIES® Port.

The success criterion at 24 weeks requires at least 70% of subjects with the TIES® Port *in situ* having no visible leakage or staining of clothing adjacent to the implant between consecutive episodes of using the lid for continence control. Spillage that might occur at opening of the lid is not regarded as leakage.

Secondary endpoints are

CLINICAL INVESTIGATION PLAN

- Absence of visible leakage or fecal staining of clothing at 16, 36 and 52 weeks.
- Proportion of implanted subjects using the TIES® Lid for continence control at 16, 24, 36 and 52 weeks.
- Subject's assessment on the ease of use of the TIES® Lid using a visual analog scale 16, 24, 36 and 52 weeks after implantation.
- Subject's preference for the TIES® solution assessed at 52 weeks.

The subject's assessment on the ease of use of the TIES® Lid will provide feedback to the manufacturer regarding future refinements of the TIES® solution. Information will be collected in the diary to understand patient's needs as described in section 10.

4.2. Durability Evaluation

Durability of use is evaluated by the cumulative proportion of subjects with the TIES® Port *in situ* at each of the following timepoints of 8, 16, 24, 36 and 52 weeks. These are secondary endpoints.

Durability will be computed by lifetable methods as the complement of the cumulative proportion of subjects in whom the TIES® Port has been removed or has spontaneously explanted, with subjects censored if they withdraw from the study with the device *in situ*, have insufficient follow-up time, or the device is removed for reasons unrelated to device performance.

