5.3.4. Withdrawal

Early termination of study participation will be documented for patients that have signed an informed consent form and who exited for any of the following reasons:

- Subject for whom the implantation procedure has been attempted but cannot completed, for example, due to technical reasons. (These subjects will be followed for six months.)
- Subject who are explanted. (These subjects will be followed for six months.)
- Subject no longer wishes to continue with the study follow-up. No further follow up applies.
- Investigator believes it is the best medical interest of the subject to discontinue study participation due to safety reasons. (These subjects will be followed until study procedure related adverse events have resolved.)
- Death of the subject.

No additional subjects will be recruited to compensate for subjects who withdraw or are withdrawn from the study.

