6.17.2. Withdrawal

Subjects may withdraw from the study at any time, with or without reason and without prejudice to further treatment. Withdrawn subjects will not undergo any additional study follow-up. The reason for withdrawal will be recorded (if given) in all cases of withdrawal. The investigator may discontinue a subject from participation in the study if the investigator feels that the subject can no longer fully comply with the requirements of the study or if any of the study procedures are deemed potentially harmful to the subject. No new data will be collected after withdrawal from the study. Data that have already been collected on withdrawn subjects will be retained and used for analysis, unless disallowed by national or local regulations.

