8.4. Investigator Reporting Responsibilities

The investigator should report to the sponsor the following events, whether expected or not, in the corresponding CRF form, with the exception of AEs / SAEs detected before the patients has signed the patient consent form.

- AE
- SAE
- Device Deficiencies that did not but might have led to a SAE if:
 - o Suitable action has not been taken or
 - o Intervention had not been made or
 - o If circumstances had been less fortunate
- New findings/updated in relation to already reported events

If an AE / SAE is present at the beginning of study prior to the subject providing signed consent to participate in the study, only its worsening should be reported.

The investigator will document all AEs on the Adverse Event Form, including (at a minimum) a description of the event, date of onset, severity, relationship to the investigational device and/or procedure, required interventions, duration, and outcome. The investigator will monitor all AEs until they are resolved, determined to be a chronic condition or the subject is lost to follow-up. The investigator will report all AEs regardless of whether it is anticipated or unanticipated and regardless of classification, seriousness, intensity, outcome or causality.

All Serious Adverse Events including all device deficiencies that could have led to a SAE should be reported to the Sponsor within 24 hours of awareness of an event via the Adverse Event electronic Case Report Form in the study's electronic database, as that will trigger an immediate e-notification to the Sponsor and Devicia. All device deficiencies should also be reported without unjustified delay.

If the e-CRF is unavailable, notification to the sponsor can be made by email and the email address is [contact]

CLINICAL INVESTIGATION PLAN

The investigator must ensure that all additional relevant information (i.e., radiology reports, hospitalization reports indicating the SAE) that becomes available is also forwarded to the sponsor immediately after the initial notification and the information should be de-identified.

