10.9. Statistical analysis

Statistical analyses will be done using SAS System®, Version 9.2 or further and a complete statistical analysis plan will be written before the conduct of analysis. All statistical analyses will be made on locked databases following data clarifications resolved due to Data Management process.

No replacement of missing data is planned in the statistical analysis.

No statistical testing will be conducted for any other parameters in the study and only descriptive analysis will be provided to fully describe the parameters recorded.

Continuous variables will be summarized using standard quantitative statistics: number of non-missing observations, mean, standard deviation, median, quartiles and range (minimum and maximum observed values). The number of missing observations will also be specified.

Categorical variables will be summarized using classical frequency statistics: number of non-missing observations and percentages by categories. Percentages will be calculated on the number of non-missing observations. The number of missing observations will also be specified.

Durability of use will be analysed using lifetable methods to allow for censoring due to subject withdrawal and device removals for reasons unrelated to device performance.

Two-sided 95% confidence intervals will be computed for all primary and secondary endpoints.

A statistical analysis plan will be written to describe all derived variables used in the reporting (especially for all parameters to be compared in time: EQ-5d and Montreux QoL questionnaire) and the statistical tables and listings to be generated.

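### The durability life table censors subjects discontinued for safety with the Port in place; this is likely informative, may overstate 52-week durability, and has no planned sensitivity analysis

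*Combined protocol and SAP*

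**What the plan says.** Section 4.2, repeated in the synopsis and in 10.6, defines the estimator: "Durability will be computed by lifetable methods as the complement of the cumulative proportion of subjects in whom the TIES® Port has been removed". Spontaneous loss of the Port counts as well, and the result is reported at 8, 16, 24, 36 and 52 weeks. The same sentence sets the censoring, "with subjects censored if they withdraw from the study with the device" in situ, and also censors short follow-up and removals unrelated to device performance. Section 10.9 repeats the approach, "using lifetable methods to allow for censoring due to subject withdrawal" and unrelated removals. Removals are thus split by reason; withdrawals are not.

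Section 5.3.4 lists the ways of leaving early. Explantation is one. A separate one reads: "Investigator believes it is the best medical interest of the subject to discontinue study participation due to safety reasons". For that group it adds: "These subjects will be followed until study procedure related adverse events have resolved". Explanted subjects, by contrast, are followed for six months.

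Section 6.17.2 also covers discontinuation by the investigator, including where study procedures are judged potentially harmful. It states: "Withdrawn subjects will not undergo any additional study follow-up", and "No new data will be collected after withdrawal from the study". Section 8.4 is broader than either: "The investigator will monitor all AEs until they are resolved, determined to be a chronic condition or the subject is lost to follow-up".

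No section plans a sensitivity analysis of the durability curve. Section 10.9 plans no replacement of missing data and defers details to an SAP still to be written.

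**The concern.** Life-table censoring is neutral only if a censored subject's later risk of Port loss equals that of the subjects still under observation. That is a strong assumption for someone taken out on safety grounds. The protocol itself connects complications with Port loss: 7.1.2 says they may lead to re-operation or to removal or replacement of the Port, and 1.5 reports Ports explanted during hernia repair in the previous studies. An above-average removal risk after a safety discontinuation is therefore the reasonable expectation, and its effect would be to push the curve upward.

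The data needed to correct this may not exist. Under 6.17.2 a later removal would not be recorded. Under 5.3.4 it could be seen while a procedure-related event is open, but nothing says whether it enters the life table. Durability is part of the primary objective (section 4) and is named in the purpose statement of 10.5, so the 52-week figure will be read as a main result.

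**Working it through.** **The plan's own figures.** The only power figures are for 24-week leakage (10.5). They reproduce with power = Φ((p − 0.60)/√(p(1−p)/n) − 1.96): for p = 0.70 and n = 200, Φ(0.10/0.0324 − 1.96) = Φ(1.126) = 87.0%, against 87% stated. All 30 cells agree within 0.5 point. They do not bear on durability, for which the documents give no target, expected rate or precision.

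**Inputs.** From the documents: N = 200 and life-table intervals ending at weeks 8, 16, 24, 36 and 52. Assumed, because the documents give nothing: R = 20 to 40 counted removals; d = 4 to 20 safety discontinuations with the Port in situ; both spread evenly over 52 weeks; removal hazard after discontinuation k = 1 to 10 times the average.

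**Step 1: the planned curve.** In each interval, survival = 1 − e/(n − c/2), with e removals, c censored and n at risk at the start. For R = 30, d = 10:

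| Interval (weeks) | n | e | c | n − c/2 | Interval survival | Cumulative |
|---|---|---|---|---|---|---|
| 0–8 | 200.0 | 4.62 | 1.54 | 199.2 | 0.977 | 0.977 |
| 8–16 | 193.8 | 4.62 | 1.54 | 193.1 | 0.976 | 0.953 |
| 16–24 | 187.7 | 4.62 | 1.54 | 186.9 | 0.975 | 0.930 |
| 24–36 | 181.5 | 6.92 | 2.31 | 180.4 | 0.962 | 0.894 |
| 36–52 | 172.3 | 9.23 | 3.08 | 170.8 | 0.946 | 0.846 |

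Planned 52-week durability is 84.6%.

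**Step 2: worst-case bound.** Count every such exit as a loss: 1 − (R + d)/200. For R = 30, d = 10 this is 1 − 40/200 = 80.0%, a gap of 4.6 points.

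| R | d | Censored | All counted as losses | Gap (points) |
|---|---|---|---|---|
| 20 | 4 | 89.9% | 88.0% | 1.9 |
| 20 | 10 | 89.7% | 85.0% | 4.7 |
| 20 | 20 | 89.4% | 80.0% | 9.4 |
| 30 | 4 | 84.8% | 83.0% | 1.8 |
| 30 | 10 | 84.6% | 80.0% | 4.6 |
| 30 | 20 | 84.2% | 75.0% | 9.2 |
| 40 | 4 | 79.8% | 78.0% | 1.8 |
| 40 | 10 | 79.4% | 75.0% | 4.4 |
| 40 | 20 | 78.8% | 70.0% | 8.8 |

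A Kaplan–Meier calculation for R = 20 gives the same percentages.

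**Step 3: between neutral and worst case.** Let S be the censored estimate and h = −ln S. With exit times even over the year and a constant hazard kh per year after exit, the chance that a discontinued subject loses the Port by week 52 is q = 1 − (1 − e^(−kh))/(kh). True durability is 1 − (R + dq)/200.

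For R = 30, d = 10: S = 0.8459 and h = 0.167. At k = 5, q = 0.32, true durability = 1 − (30 + 3.2)/200 = 83.4%, and the overstatement is 1.2 points. Across k:

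| k | 1 | 2 | 3 | 5 | 10 |
|---|---|---|---|---|---|
| Overstatement (points) | 0.0 | 0.3 | 0.7 | 1.2 | 2.2 |

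Over the whole grid at k = 2 to 10, the smallest value is 0.1 point (R = 20, d = 4, k = 2) and the largest 5.0 points (R = 40, d = 20, k = 10).

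**Step 4: follow-up rules side by side.** For a safety discontinuation, 5.3.4 ends follow-up when procedure-related events resolve and does not mention device-related events; 6.17.2 allows no further follow-up or data; 8.4 follows all adverse events. The three cannot all apply, and none asks for Port status to week 52.

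**The case against.** A reader might infer that one-year durability is overstated, and that a removal soon after discontinuation is never counted. The documents support neither as a fact. They do not say how many subjects will leave this way or how often they lose the Port afterwards, and at the average hazard the censored curve is unbiased. A safety reason need not concern the device. The plan also keeps many device problems inside the study: revision, a second implant and explantation are all allowed on the investigator's assessment, and a removal before withdrawal already counts unless unrelated to device performance. The group could be small and include unrelated illness. A removal could also be observed under 5.3.4 or 8.4 while an event is open. What is missing is narrower: a consistent follow-up rule and a rule on whether such a removal counts.

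The worst-case gap should not be read as the expected bias. Moderate hazards give 0.3 to 1.2 points in the middle scenario (k = 2 to 5), against a 95% half-width of about 4.2 points at 90% durability (1.96 × √(0.9 × 0.1/200)). Durability endpoints are secondary, descriptive and without a threshold, and the SAP yet to be written could add a sensitivity curve.

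These points limit the size and certainty of the concern. They do not remove it: the censoring rule is explicit and ignores the reason for leaving, nothing planned tests it, and Port status not collected after exit may not be recoverable later.

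**Conclusion.** The concern holds in conditional form. The written rule censors safety discontinuations with the Port in situ as though they were uninformative, which they probably are not. The 52-week figure may therefore be too high: by about 0.1 to 5.0 points at 2 to 10 times the average hazard, and by at most about 2 to 9 points if every such exit is a loss. Both ranges rest on the assumed 20 to 40 removals and 4 to 20 exits per 200, evenly spread in time; with no such exits, or an average hazard after exit, there is no bias. The conflict between 5.3.4 and 6.17.2 is textual and needs no assumption. The change is worth making because it is cheap and durability is part of the primary objective, but no pass/fail result depends on it.

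**What to change.** 1. Keep the planned curve. In 4.2, 10.6 and the SAP, add a prespecified sensitivity curve that counts each discontinuation with the Port in situ for a device- or procedure-related safety reason as a failure on its date. Limiting it to those reasons keeps it consistent with the plan's censoring of removals unrelated to device performance.
2. Reconcile 5.3.4 with 6.17.2 and 8.4 on what is followed and recorded after a safety discontinuation, including device-related events.
3. Where the subject consents, record Port status to week 52 (in situ, or removed with date and reason). This is a new data item: the follow-up now in 5.3.4 does not reach week 52, and 6.17.2 as written would prohibit it. State that an observed device-related removal is an event on its date.

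Cost: protocol and SAP wording, a small amount of added follow-up for a few subjects, one extra curve, and a durability figure that may be less favourable.
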